10.2.5. WOUND HEALING AND ULCER MEASUREMENT

Based on photographs and measurements of ulcers, the length and width (in cm) of the ulcer will be recorded by the wound core lab. Additionally, the area of the open ulcer (in cm^2) will be measured by the wound core lab. If an ulcer is determined to be 100% healed, the area of the ulcer will be set to 0. Descriptive statistics of the sum of ulcer areas and change from baseline will be performed by treatment arm and visit. The number of subjects with a 100% healed ulcer will be summarized by visit and treatment arm using the method for categorical variables.

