6.2.2. SECONDARY EFFICACY ENDPOINTS

Other secondary endpoints will include:

- Difference in pain level between baseline and the 9 month follow-up as determined by VAS by sex and by comorbidities (esp. diabetes or renal dysfunction)
- Change in tissue oxygenation (TcPO₂) from baseline to 6, 9 and 12 months following the first treatment
- Change in hemodynamic measures (ABI and TBI) from baseline to Day 28, Day 90, 6 months, 9 months and 12 months following the first treatment
- Change in perfusion (MRA) from baseline to 9 months following the first treatment
- Wound healing (no ulcer: change of skin condition, one ulcer: change of ulcer size, multiple ulcer: change of ulcer number) from baseline to 9 months following the first treatment
- Change in VAS score from baseline to Day 14, Day 28, Day 42, Day 90, at 6 months, 9 months, and 12 months.
- Change in QOL score (VascuQol) at 90 Days, 9 months and 12 months;
- Major limb amputation rate at six months and twelve months following the first treatment
- Mortality at six and twelve months after first treatment

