2.2. Secondary Objectives

The secondary objective of the study is to evaluate potential bioactivity of IM administration of VM202 in subjects with CLI, when compared to placebo, on:

- Change in VAS for pain at rest
- Leg ulcer healing (as assessed by ulcer surface area and time to complete healing)
- Hemodynamic assessment (ABI/TBI)
- Tissue oxygenation ($TcPO_2$)
- Incidence and extent of lower leg amputation, limb salvage or other surgical interventions
- VascuQoL
- Perfusion (MRA)

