5.2. Statistical Methods

Two-sided p -values < 0.05 will be considered statistically significant, unless otherwise stated.

Separate statistical tests will be performed at each time point for key endpoints of interest.

In general, an overall test to determine if there is a statistically significant difference among the three treatment arms will be conducted first. Further comparisons will be made to determine if either the low or high dose groups are significantly different from the placebo group.

For continuous variables, a one-way analysis of variance (ANOVA) with treatment group (high dose, low dose, and placebo) as a factor will be used to determine if there is a significant difference among the groups. The low and high dose groups will each be compared against the placebo group using Dunnett's test. The mean difference between the VM202 groups versus placebo along with 95% confidence intervals for the mean difference will also be presented. To be viewed as secondary, an additional set of analyses will be run using non-parametric tests. A Jonckheere-Tepstra test will be applied to the VAS change from baseline results to detect overall trend differences. Non-parametric pairwise treatment comparisons versus placebo will also be made using Wilcoxon Rank Sum test. Within each treatment group for each endpoint, both a paired t-test (parametric) and Wilcoxon Signed Rank test will be run to test for differences comparing baseline to each post-baseline assessment.

For categorical variables, Fisher's exact test will be used to determine if there is a significant difference among the three treatment groups. Separate Fisher's exact tests will be used to compare the low and high dose groups to the placebo group.

For time-to-event variables (such as amputation, limb salvage and mortality), Kaplan-Meier estimates will be used to estimate survival times. Differences in survival times will be compared among groups using the log-rank test.

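### Ulcer area, named for comparison with placebo, gets no between-arm difference, confidence interval or test; only complete healing is compared

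*SAP*

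**What the plan says.** SAP 2.2 sets out to evaluate bioactivity against placebo on a list of measures that includes "Leg ulcer healing (as assessed by ulcer surface area and time to complete healing"). Protocol 6.2.2 lists wound healing from baseline to 9 months as a secondary endpoint, defined by ulcer status: "one ulcer: change of ulcer size, multiple ulcer: change of ulcer number".

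SAP 10.2.5 has a core lab measure open ulcer area in cm², with a healed ulcer set to 0. For area it then says "Descriptive statistics of the sum of ulcer areas and change from baseline will be performed by treatment arm and visit". For healing it says "The number of subjects with a 100% healed ulcer will be summarized by visit and treatment arm using the method for categorical variables". SAP 5.2 defines that categorical method: Fisher's "exact test will be used to determine if there is a significant difference among the three treatment groups", followed by separate Fisher tests of each dose against placebo.

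The shells agree with the text. Table 9.1.1 (Wound Area) has N, mean, SD, median, minimum and maximum for the result and its change, and nothing else. Table 9.2.1 has an overall Fisher p-value and one per dose, restricted to subjects with a baseline ulcer.

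**The concern.** The measure is named for comparison with placebo and collected at each visit from Day 0 to Month 12, but the plan never compares it. For the other continuous efficacy measures (VAS, TcPO₂, ABI, TBI, VascuQoL, Rutherford class) the shells carry a model-based difference, a 95% CI, Dunnett p-values and rank tests. MRA is the one exception, and there the SAP expressly rules out tests.

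The healed/not-healed split scores an ulcer that is almost closed the same as one that has grown. Rest pain alone can qualify a patient for entry, so the ulcer subset may be well below 20:20:10, and an exact test on a binary outcome is weak at such sizes. SAP 4 says the trial was sized to estimate effects and variability for a pivotal study. A report with no stated area contrast against placebo serves that purpose poorly.

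**Working it through.** **1. What the plan's own numbers supply.** The only power figure is for pain: means 30, 28 and 10, SD 25, n = 20:20:10, stated power 49%. The weighted mean is (20×30 + 20×28 + 10×10)/50 = 25.2. The noncentrality is (20×4.8² + 20×2.8² + 10×15.2²)/25² = 2928/625 = 4.685. The noncentral F with 2 and 47 df gives 45.1%; the large-sample chi-square form gives 47.7%. The 49% is not at issue here. All that is borrowed is the standardized effect of 16 mg against placebo: (30 − 10)/25 = 0.8.

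**2. Assumptions, because the plan gives none for ulcers.** Each ulcer patient has a normal healing score, shifted by 0.8 SD on active drug. The ulcer is healed above a threshold set by the placebo healing rate; below it, the remaining fraction of baseline area falls as the score rises. Placebo healing of 10, 20, 30 and 40% then implies 32, 48, 61 and 71% on 16 mg. Tests are two-sided at 5% with no multiplicity adjustment, as the SAP plans for both Fisher and Wilcoxon.

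**3. Fisher by hand, 10 vs 5, placebo healing 20%.** In favour of active drug, significance needs at least 6/10 vs 0/5 (p = 0.044), at least 9/10 vs 1/5 (p = 0.017) or 10/10 vs 2/5 (p = 0.022). With 48.3% healing on active:
- P(0/5) × P(≥6/10) = 0.328 × 0.337 = 0.110
- P(1/5) × P(≥9/10) = 0.410 × 0.0081 = 0.003
- P(2/5) × P(10/10) = 0.205 × 0.0007 = 0.0001

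The total is about 11%.

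**4. Range over placebo healing of 10–40%** (Fisher on healed; Wilcoxon on fraction of baseline area remaining, by simulation):

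| Ulcer patients, 16 mg vs placebo | Fisher | Wilcoxon |
|---|---|---|
| 10 vs 5 | 3–13% | 22–25% |
| 14 vs 7 | 5–18% | 31–33% |
| 20 vs 10 | 12–30% | 42–48% |

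Under no effect, Fisher rejected in 0.3–3.3% of trials and Wilcoxon in 3.7–5.0%, so part of the gap is Fisher's conservatism.

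**5. Dependence on the area scale.** Take 20 vs 10, 20% placebo healing and a lognormal baseline area (assumed). A t-test on raw cm² change has about 38% power at log SD 0.5 but about 20% at log SD 1.0, against about 24% for Fisher. At log SD 1.0 with 20–40% healing, a t-test on raw change has about 15–20% power and a Wilcoxon test on raw change about a quarter, against 25–30% for Fisher. Only at 10% healing do both raw-area tests beat Fisher at that skew.

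**The case against.** Several points on the other side have force.

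- A reader might infer that the plan about halves the power of its ulcer comparison. The documents do not support that. They give no ulcer effect, variance, healing rate or patient count. A halving is a mid-range result under borrowed inputs and one choice of scale. SAP 10.2.5 summarises raw cm² change, where the advantage can vanish. The model in the working also favours area by construction: one noise-free score drives both healing and remaining area, with no measurement error, new ulcers, amputations or deaths.
- A reader might infer that the ulcer-size data are thrown away. They are not. Table 9.1.1 shows area and its change by arm at every visit, and a raw mean difference could be worked out from it.
- Complete healing is not an arbitrary cut. SAP 2.2 names time to complete healing beside surface area, so the healed comparison has its own standing.
- For multiple ulcers the protocol endpoint is change in number, so a summed-area comparison for everyone is not that endpoint.
- In a small Phase II trial, descriptive handling of a subset measure is defensible, as with MRA.

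The general rule in SAP 5.2 that for continuous variables "a one-way analysis of variance (ANOVA) with treatment group (high dose, low dose, and placebo) as a factor will be used" might be read to cover area. But 10.2.5 invokes a method only for the healed count, and the shell has no rows for an area test. If coverage was intended, both need correcting. None of these points supplies the missing contrast.

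**Conclusion.** The gap is real and can be read directly from the text: ulcer area is named for comparison with placebo, and no between-arm difference, interval or test is planned for it. The size of the loss is conditional. With a 0.8 SD effect, 10–40% placebo healing and fraction of baseline area as the scale, the rank test adds about 10 to 35 percentage points over Fisher across the cases shown. On raw cm² change with skewed baselines it adds little or nothing unless healing is rare. Even the better test has only 22–25% power at 10 vs 5, so the main gain is an estimate with an interval, not a likely significant result. This justifies adding an area comparison beside the healed proportion. It does not justify replacing the healed proportion.

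**What to change.** Keep the Fisher comparison of 100% healed. Add to SAP 10.2.5, and as rows in Tables 9.1.1 and 9.1.2, one 9-month comparison of each dose with placebo among subjects with a baseline ulcer. The outcome is total ulcer area as a fraction of baseline area (healed = 0). Use the rank test already in SAP 5.2 ("Non-parametric pairwise treatment comparisons versus placebo will also be made using Wilcoxon Rank Sum test"), with a Hodges-Lehmann difference and 95% CI.

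State three further things in 10.2.5:
- How subjects with missing 9-month area, major amputation or death are ranked, for example amputation and death as worst rank. Unlike 10.2.1–10.2.3, 10.2.6 and 10.2.8, this section has no such rule, and the healed table has none to borrow. It matters most in the ITT table, because the per-protocol set already requires a 9-month VAS.
- That the summed-area fraction supplements the protocol's change-in-number endpoint for subjects with several ulcers.
- Whether healed means any or all of a subject's ulcers.

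The cost is a few sentences and table rows before unblinding, with no new data. The downside is one more unadjusted secondary p-value per dose, at low power; restricting the test to 9 months limits this.

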10.2.6. QUALITY OF LIFE (VASCUQoL)

The VascuQoL contains five domains (activity, symptom, pain, emotion and social functioning). Each domain is scored on a scale from 1 to 7 based on the VascuQoL manual.

Scores will be assigned to responses according to the following table:

VascuQoL Question(s)	Score Assigned= Response
1, 2, 5, 6, 7, 12, 13, 17, 19, 21, 23, 25	1= All of the time; 2= Most of the time; 3= Much of the time; 4= Some of the time; 5= A little of the time; 6= Hardly any of the time; 7= None of the time
3, 8, 20	1= A very great deal of discomfort or distress; 2= A great deal of discomfort or distress; 3= A good deal of discomfort or distress; 4= A moderate amount of discomfort or distress; 5= Some discomfort or distress; 6= Very little discomfort or distress; 7= No discomfort or distress
4	1= Total limited, couldn't exercise at all; 2= Extremely limited; 3= Very limited; 4= Moderately limited; 5= A little limited; 6= Only very slightly limited; 7= Not at all limited
9	1= Not at all; 2= A little; 3= Somewhat; 4= Moderately; 5= A good deal; 6= A great deal; 7= A very great deal
10	1= Total limited, couldn't walk at all; 2= Extremely limited; 3= Very limited; 4= Moderately limited; 5= A little limited; 6= Only very slightly limited; 7= Not at all limited
11, 24	1= A very great deal; 2= A great deal; 3= A good deal; 4= Moderately; 5= Somewhat; 6= A little; 7= Not at all
14	1= Total limited, couldn't climb stairs at all; 2= Extremely limited; 3= Very limited; 4= Moderately limited; 5= A little limited; 6= Only very slightly limited; 7= Not at all limited
15	1= Total limited, couldn't socialize at all; 2= Extremely limited; 3= Very limited; 4= Moderately limited; 5= A little limited; 6= Only very slightly limited; 7= Not at all limited
16	1= Total limited, couldn't perform housework; 2= Extremely limited; 3= Very limited; 4= Moderately limited; 5= A little limited; 6= Only very slightly limited; 7= Not at all limited
18	1= Severely limited; 2= Very limited; 3= Moderately limited; 4= Slightly limited; 5= Very slightly limited; 6= Hardly limited at all; 7= Not limited at all
22	1= Total limited, couldn't go shopping at all; 2= Extremely limited; 3= Very limited; 4= Moderately limited; 5= A little limited; 6= Only very slightly limited; 7= Not at all limited

The domain score is the total of the non-missing scores in the domain divided by the number of responded questions in the domain. The total King's College Hospital's VascuQol score is the total non-missing score divided by the total number of responded questions.

The following question numbers represent the various domains.

Domain	VascuQoL Questions
Activity	4, 9, 10, 14, 16, 18, 22, 24
Symptom	3, 5, 8, 17
Pain	1, 7, 13, 20
Emotional	2, 11, 12, 19, 21, 23, 25
Social	6, 15

Each QoL domain , the King's College Hospital's VascuQol score and each individual question will be summarized by treatment arm and study visit by the methods for continuous variables. Change from baseline will be also be summarized .

10.2.6.1 Imputation Methods of VASCUQOL Results for the ITT Population

For subjects without the efficacy endpoint (VASCUQOL change from baseline to any post baseline result), the following imputation methods will be applied:

- For missing Baseline VASCUQOL, assign the VASCUQOL score at Screening if the VASCUQOL score score at Day 0 is missing.
- For any post baseline VASCUQOL, assign the post baseline VASCUQOL score prior to the missing post baseline VASCUQOL via the last observation carried forward (LOCF) method.

For subjects who had a major amputation or limb procedure carried out, the following imputation methods will be applied:

- For subjects with a major amputation, assign the VASCUQOL score prior to the amputation.
- For subjects with a limb salvage, assign the VASCUQOL score prior to the intervention.

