1.3.3. UNMET CLINICAL NEED

In the absence of revascularization options, most patients with CLI require amputation within 6 months. Patients requiring major amputation face a diminished quality of life, an unfavorable natural history and need extensive resources for their post-amputation rehabilitation and course. The 1-year amputation-free survival rate for patients diagnosed with CLI is 45%; the mortality rate is approximately 25% and may be as high as 45% in those who have undergone amputation.^{1,6,16} Management of this end-stage disease process consumes a significant amount of healthcare resources.^{17,18} Clearly, new therapeutic approaches are required.

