4.2.8. PATIENT QUESTIONNAIRE (VASCUQOL)

The VascuQol patient questionnaire was specifically developed for use in patients with lower limb ischemia.⁴² This questionnaire has 25 questions that review five domains: activity level, symptoms, pain, emotional status and social items. VascuQol was found to be better at detecting improvement in symptoms, disease severity than SF-36 in CLI patients and correlated well with the Rutherford classification.⁴³ This test will be administered pre-injection on Day 0, at Day 90, 9 months, and 12 months. The VascuQol can be found in Appendix 5.

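### On its plain reading, SAP 10.2.6.1 replaces VascuQoL scores reported after a major amputation with the pre-amputation score, so the ITT result is not quality of life at the scheduled visits

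*SAP*

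**What the plan says.** Protocol 6.2.2 lists as a secondary endpoint "Change in QOL score (VascuQol) at 90 Days, 9 months and 12 months". Protocol 4.2.8 fixes the visits: "This test will be administered pre-injection on Day 0, at Day 90, 9 months, and 12 months". SAP 10.2 analyses the secondary endpoints in both the per-protocol (PP) and the ITT population.

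SAP 10.2.6.1, headed as applying to ITT, has two blocks.

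- The first opens "For subjects without the efficacy endpoint (VASCUQOL change from baseline to any post baseline result), the following imputation methods will be applied". It uses a Screening score for a missing baseline and last observation carried forward (LOCF) for a missing post-baseline score.
- The second opens "For subjects who had a major amputation or limb procedure carried out, the following imputation methods will be applied". Its first bullet is "For subjects with a major amputation, assign the VASCUQOL score prior to the amputation". Its second bullet treats limb salvage the same way.

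Neither bullet of the second block mentions missing scores. Protocol 1.3.3 says of the patients concerned: "Patients requiring major amputation face a diminished quality of life, an unfavorable natural history".

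**The concern.** The endpoint is the patient's quality of life at three fixed times. An ABI or TcPO2 cannot be taken on a limb that is gone, but a patient can still answer a questionnaire after amputation. By the domain table in SAP 10.2.6, activity, emotional and social items make up 8 + 7 + 2 = 17 of the 25 questions.

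The section looks carried over from the limb measures. Its amputation bullet matches those for TcPO2 and ABI/TBI (SAP 10.2.2.1 and 10.2.3.1), and its baseline bullet relies on a Screening VascuQoL that neither Protocol Appendix 1 nor SAP Table 2 schedules.

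If reported scores are replaced, the ITT mean no longer depends on what amputees say afterwards. Any effect of VM202 on quality of life that runs through amputation, in either direction, then drops out of the ITT comparison. The PP and ITT tables in the 10.x series would also differ in what they measure, not only in whom they include.

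**Working it through.** The documents give no figure for this point, so there is nothing to reproduce. The check is of the text, followed by an illustration on stated assumptions.

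**1. Is the rule limited to missing scores?** The first block is limited by its lead-in to subjects lacking the endpoint. The second is triggered by the procedure alone. On the wording, a reported score is replaced.

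**2. Will there be reported scores to replace?** Protocol 3.4.11, 3.4.13 and 3.4.14 schedule VascuQoL at Day 90, 9 and 12 months. Protocol 3.5.2 does not list amputation among the possible reasons for discontinuation, and Protocol 6.2.2 follows amputation to 12 months. So some amputees can have later scores.

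**3. What value is assigned?** The only scores are at Day 0, Day 90, 9 and 12 months.

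| Amputation occurs | Score assigned afterwards | Change from baseline |
|---|---|---|
| Before Day 90 | Day 0 | exactly 0 at Day 90, 9 and 12 months |
| Day 90 to month 9 | Day 90 | Day-90 change repeated at 9 and 12 months |
| Month 9 to month 12 | month 9 | month-9 change repeated at 12 months |

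The VAS rule in SAP 10.1.2 specifies a post-baseline score. The VascuQoL bullet does not, so Day 0 qualifies.

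**4. Bias.** Let p be the share of an arm with an amputation and a later score, and d the post- minus pre-amputation change. The rule shifts the arm mean by −p × d. If d is the same in both arms, the bias in the VM202 minus placebo difference is

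(p_placebo − p_VM202) × d.

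If d differs by arm, the bias is p_placebo × d_placebo − p_VM202 × d_VM202. It is zero when shares and changes are equal.

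**5. Illustration (all inputs assumed).** One dose arm of 20 with 2 amputees, placebo of 10 with 3; non-amputees change by +0.5 in both arms; amputees stood at a change of 0 before amputation. For d = −1.5:

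- Reported scores: placebo (7 × 0.5 + 3 × (−1.5))/10 = −0.10; VM202 (18 × 0.5 + 2 × (−1.5))/20 = +0.30; difference 0.40.
- SAP rule: placebo (7 × 0.5 + 3 × 0)/10 = 0.35; VM202 (18 × 0.5 + 2 × 0)/20 = 0.45; difference 0.10.
- Check: (0.30 − 0.10) × (−1.5) = −0.30, and 0.40 − 0.30 = 0.10.

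| Assumed d (points, 1–7 scale) | Difference, reported scores | Difference, SAP rule | Bias |
|---|---|---|---|
| −2.0 | 0.50 | 0.10 | −0.40 |
| −1.5 | 0.40 | 0.10 | −0.30 |
| −1.0 | 0.30 | 0.10 | −0.20 |
| −0.5 | 0.20 | 0.10 | −0.10 |
| +0.5 | 0.00 | 0.10 | +0.10 |

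The rule returns 0.10 whatever the amputees report.

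**6. What if later scores are missing?** In the d = −1.5 example, suppose no amputee has a later questionnaire. Dropping all of them gives 0.5 − 0.5 = 0.00, further from 0.40 than the 0.10 under the current rule. Omission is therefore no safe substitute.

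**The case against.** **Replacement is inferred.** The section is headed as imputation and never says that observed scores are overwritten. A missing-only reading is not empty: the LOCF bullet carries only post-baseline scores, so the amputation bullet would still supply Day 0 for an amputee with none. The layout note for Table 10.1.2 also omits the reference to imputation rules given for VAS, TcPO2 and ABI/TBI. This justifies saying plain reading rather than certainty. It does not rescue the rule. The lead-in has no missing-score condition, and the note for Table 12.2 omits the same reference although SAP 10.2.8.1 sets rules for it. Even read as missing-only, the bullet conflicts with LOCF: for an amputation between Day 90 and month 9, with month 9 reported and month 12 missing, LOCF gives the month-9 score and the amputation bullet gives Day 90.

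**Direction.** A reader might infer that the rule necessarily hides a loss. Protocol 1.3.3 points that way but reports no VascuQoL result. Protocol 1.3.2 says amputation removes the origin of rest pain, and item 17 takes its best score when there are no ulcers. Of the 17 activity, emotional and social items, 13 refer to the leg or foot or its poor circulation, so their meaning after limb loss is unclear. This objection stands on the sign. It is no reason to discard the reported score.

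**Size.** Protocol 1.3.3 gives 1-year amputation-free survival of 45% and mortality of about 25%. A reader might infer that 75% − 45% = 30%, or 15 of 50 patients, would be affected. Those are general CLI figures. This trial takes Rutherford 4 or 5 only and excludes expected amputation within 4 weeks, active infection and life expectancy under 6 months. Some amputees may leave the study, and the early-withdrawal visit has no VascuQoL. So 15 is at most an upper bound.

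**Concealment.** A reader might infer that harm from amputation would go unseen. It would not: SAP 10.2.7 analyses amputation, limb salvage and mortality separately, Listing 24 shows every answer, and PP, the primary efficacy set, has no such rule. None of this repairs the ITT VascuQoL estimate.

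**Conclusion.** The concern holds for the ITT analysis of this one secondary endpoint. On its plain reading, SAP 10.2.6.1 substitutes a pre-amputation score for whatever an amputee later reports, and a change of exactly 0 when the amputation precedes Day 90. The ITT result therefore does not describe quality of life at Day 90, 9 or 12 months and is not comparable in meaning with the PP tables.

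The bias equals the difference in amputee share times the post- minus pre-amputation change. The documents supply neither its size nor its sign for each domain. The −0.40 to +0.10 points shown rest on assumed shares of 30% and 10% and assumed changes of −2.0 to +0.5. The documents do not support a claim that the rule is certain to work against VM202, or that a particular number of patients is affected.

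**What to change.** In SAP 10.2.6.1:

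1. State that ITT uses the reported VascuQoL score at each visit whether or not a major amputation has occurred, and that assigned values, from the amputation bullet or LOCF, apply only where the score is missing.
2. Report by arm the number of amputees with and without a post-amputation score.
3. Do not simply drop amputees whose later score is missing. Show the result under the current pre-amputation carry-forward and under a less favourable assigned value, both as labelled sensitivity analyses.
4. Apply the observed-score principle to the limb-salvage bullet, which has the same lead-in and effect, or state why it differs.
5. Align the Table 10.1.2 layout note with the revised text.

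Deleting the amputation bullet alone would not be enough, because LOCF would still carry a pre-amputation score across the amputation to a missing visit. The cost is a short SAP edit and one or two extra ITT tables for a secondary endpoint. The questionnaires are already scheduled, so no new data are needed.
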